Protocol n°: UC-GIG-2203 EudraCT n°: 2022-000273-81

PROTOCOL SUMMARY

A) TRIAL IDENTIFICATION

Sponsor – protocol code number: PRODIGE 73 – UCGI 40

Version (Number & date): V1.1 - 11 AUGUST 2022

Trial title: Randomised phase II study evaluating trifluridine/tipiracil plus oxaliplatin versus FOLFOX in patients with gastric, oesophagus or gastroesophageal junction adenocarcinoma locally advanced, recurrent or metastatic, ineligible for triplet chemotherapy

Phase (for trials on medicinal products): II

Trial title for lay people: Oxaliplatin in combination with trifluridine/tipiracil or 5-fluorouracile in frail patients with advanced, recurrent or metastatic gastric, oesophageal or gastroesophageal junction cancer

Abbreviated title: PRODIGE 73 – UCGI 40 – LOGICAN

Coordinating investigator: [name] [name]

Number of centres (estimate): 21 Number of patients randomised: 118

B) SPONSOR IDENTIFICATI	ON
Name:	UNICANCER [name] (France)
Contact person:	[name] [name] Project Manager UNICANCER [contact] [contact] email: [contact]

Protocol n°: UC-GIG-2203 EudraCT n°: 2022-000273-81

C) TRIAL GENERAL INFORMATION

Indication:

Patients with gastric, oesophagus or gastroesophageal junction adenocarcinoma locally advanced, recurrent or metastatic, ineligible for triplet chemotherapy (e.g. DCF, EOX, ECX, EOF, ECF, TFOX).

Patients ineligible for triplet chemotherapy are patients with ECOG-PS=2 or age ≥70 years old plus one frailty criteria on ADL or IADL score or patients presenting a denutrition defined by albumin <30 g/l.

The reason of ineligibility to triplet chemotherapy will be collected in the CRF.

Trial description/design:

Randomized, open label, comparative, multicentric, phase II trial comparing Trifluridine/Tipiracil + oxaliplatin vs FOLFOX regimen as first-line palliative therapy

Primary objective:

The primary objective is to evaluate the superiority of trifluridine/tipiracil + oxaliplatin over FOLFOX regimen in terms of Progression-Free Survival (PFS), in first-line palliative setting, in patients with gastric, oesophagus or gastroesophageal junction adenocarcinoma locally advanced, recurrent or metastatic, ineligible for triplet chemotherapy.

Secondary objectives:

The secondary objectives are the evaluation of:

- The efficacy of the treatments in terms of:
 - Objective Response rate (according to RECIST v1.1) (ORR)
 - Overall Survival (OS)
- Safety and tolerability of treatment (NCI-CTCAE version 5.0)
- Time to PS deterioration >2
- The effect of treatments on Quality of Life (QoL)

Ancillary studies:

To evaluate prognostic and predictive values of several biological and radiological biomarkers. A correlation with Geriatric Core Dataset (G-CODE) and overall treatment utility (OTU) (Hall's index) will also be studied in patients ≥70 years old.

Protocol n°: UC-GIG-2203 EudraCT n°: 2022-000273-81

Diagnosis and Inclusion criteria:

- 1. Histologically confirmed locally advanced, recurrent or metastatic non resectable adenocarcinoma of the stomach, oesophagus or gastroesophageal junction (GEJ) ineligible to curative treatment and ineligible to immunotherapy (CPS <5 or patient presenting any contraindication preventing the use of immunotherapy).
- 2. No dysphagia or difficulty in swallowing.
- No overexpression/amplification of HER2 (IHC 0 or 1+; if IHC is 2+, HIS must be negative).
 Known CPS PD-L1 score (result in % with the name of the method used). The microsatellite
 and MMR status of patient's tumour (MSI/MSS and pMMR/dMMR) must also be known at the
 time of screening (IHC and PCR tests have to be done).
- 4. At least one evaluable lesion according to RECIST v1.1 outside any previously irradiated area.
- 5. No prior palliative chemotherapy.
- 6. Age ≥18 years old.
- 7. Patient unfit for triplet chemotherapy = ECOG-PS=2 or age ≥70 year old **PLUS** one frailty criteria on ADL/IADL score or denutrition defined by albumin <30 g/L

The reason of ineligibility to triplet chemotherapy will be collected in the CRF.

- 8. Adequate organs function:
 - ✓ Absolute neutrophils count ≥1.5x10⁹/L
 - ✓ Platelets count ≥100x10⁹/L
 - √ Haemoglobin ≥9 g/L
 - ✓ Serum bilirubin levels <2 times upper limit of normal (ULN), up to 2.5 times ULN in case of hepatic metastasis (biliary drainage allowed)
 - ✓ Transaminases <5 times ULN

 - ✓ Creatinine clearance >40 mL/min
- 9. No Dihydropyrimidine dehydrogenase (DPD) deficiency (uracilemia <16 ng/ml)
- 10. Women of childbearing potential must have a negative serum or urine pregnancy test done within 14 days before the first study treatment.
- 11. Patients must agree to use adequate contraception methods for the duration of study treatment and within 6 months after completing treatment.
- 12. Patients must be affiliated to a Social Security System (or equivalent).
- 13. Patient must have signed and dated a written informed consent form prior to any trial specific procedures. When the patient is physically unable to give their written consent, a trusted person of their choice, independent from the investigator or the sponsor, can confirm in writing the patient's consent.
- 14. Availability of archived tumour material for ancillary studies

R3 DOC 45 - Version 5 du 07/11/2018

Protocol n°: UC-GIG-2203 EudraCT n°: 2022-000273-81

Non-inclusion criteria:

- 1. Patient with a performance status ECOG PS >2.
- 2. Other current or previous malignancy within the past 3 years (with the exception of squamous cell carcinoma of the skin treated by surgery).
- 3. Adjuvant chemotherapy or radio-chemotherapy completed for less than 6 months.
- 4. Peripheral neuropathy of NCI-CTCAE grade ≥2 at baseline.
- 5. Patients with known allergy or severe hypersensitivity to any of the trial drugs or any of the trial drug excipients.
- 6. Patients unwilling or unable to comply with trial obligations for geographic, social, or physical reasons, or who are unable to understand the purpose and procedures of the trial.
- 7. Previous treatment with trifluridine/tipiracil.
- 8. Known Human Immunodeficiency Virus (HIV) infection.
- 9. Active Hepatitis B virus (HBV, defined as having a positive hepatitis B surface antigen [HBsAg] test prior to inclusion) or hepatitis C virus (HCV).
- 10. Interstitial lung disease.
- 11. Prior pneumonitis requiring systemic corticosteroid therapy.
- 12. Active infections.
- 13. Pregnant or breastfeeding woman.
- 14. Participation in another therapeutic trial within the 30 days prior to randomisation.
- 15. Persons deprived of their liberty or under protective custody or guardianship.
- 16. Clinically relevant coronary artery disease or history of myocardial infarction in the last 12 months, or high risk of uncontrolled arrhythmia (for men: QTc ≥450 msec, for women: QTc ≥470 msec)

Primary endpoint:

PFS defined as the time from the date of randomisation to date of disease progression (radiological or clinical) or death from any cause, whichever occurs first. Patients without tumour progression or death at the time of analysis will be censored at the date of their last tumour assessment.

Protocol n°: UC-GIG-2203 EudraCT n°: 2022-000273-81

Secondary endpoint(s):

- Efficacy endpoints:

- ORR (according to RECIST v1.1) defined as the percentage of patients with Complete Response (CR) or Partial Response (PR). Patients who discontinue treatment without a tumour assessment will be considered non-responders for the analysis
- Overall survival (OS), defined as the time from date of randomisation to the date of death from any cause. Patients alive at the database cut-off date will be censored at the last date of follow-up.
- Safety and tolerability of treatment (NCI-CTCAE version 5.0) determined through the incidence of adverse events, treatment related adverse events, serious adverse Events (SAE), and death.
- Time to PS deterioration >2 defined as the time between patient randomisation and the first date when PS>2
- Quality of Life (QoL) according to QLQ-C30 questionnaire
- Ancillary studies will address:
 - Specific pathological features and expression of biomarkers: microsatellite status (MS), PD1 and PDL1 expression, TMB, CD8+ cell infiltration, Epstein Barr Virus (assessed by in situ hybridization), TP53, E-cadherin, HER3.
 - Circulating tumour DNA (ctDNA) and its value for prognosis and treatment monitoring (monitoring of DNA levels at different point during the treatment: pretreatment ctDNA and then every two months during the first year or till disease progression whatever occurs first). Genetic changes on several genes will also be evaluated.
 - Correlation of Geriatric Core Dataset (G-CODE) (including social assessment, functional autonomy, mobility, nutrition, cognition, mood and comorbidity analysis) and Overall survival.
 - Correlation of different biological prognostic scores (Glasgow and modified Glasgow Prognostic Score (GPS; mGPS), NLR (Neutrophil to Lymphocyte Ratio) with patient outcome.

Protocol n°: UC-GIG-2203 EudraCT n°: 2022-000273-81

D) INVESTIGATIONAL MEDICINAL PRODUCTS

PRODUCT NAMES AND ADMINISTRATION:

Drug name (INN)	Registered name ⁽¹⁾	Pharmaceutical form	Administration route	Posology	
Trifluridine/Tipiracil 15mg/6.14 mg	Lonsurf®	Film-coated tablet	Oral	35 mg/m² BID for 5 days (D1=D15)	
Trifluridine/Tipiracil 20mg/8.19 mg	Lonsurf®	Film-coated tablet	Oral	35 mg/m ² BID for 5 days (D1=D15)	
5FU	-	Concentrate for solution for infusion	Intravenous (IV)	46-hour continuous infusion 5-FU 2400 mg/m² at day1, every 14 days	
5FU	-	Concentrate for solution for infusion	Intravenous (IV)	Bolus 5-FU 400 mg/m² at day 1, every 14 days	
Capecitabine	-	Film-coated tablet	Oral	1000 mg/m² BID during 2 weeks, every 3 weeks	
Oxaliplatin	-	Concentrate for solution for infusion	Intravenous (IV)	70-85 mg/m² at day 1, every 14 days	
Folinic acid	-	Solution for injection or infusion	Intravenous (IV)	400 mg/m² at day 1, every 14 days	
L-folinic acid	-	Solution for injection or infusion	Intravenous (IV)	200 mg/m² at day 1, every 14 days	

⁽¹⁾ When any generic drug can be is used indicate only the INN name. The choice of the registered name or brand name used in the trial is at the investigation centre discretion.

Protocol n°: UC-GIG-2203 EudraCT n°: 2022-000273-81

Therapeutic regimens:

[figure not shown]
ARM A: Experimental group (Trifluridine/Tipiracil + Oxaliplatin)

Trifluridine/Tipiracil will be administered with a 14-day schedule (35 mg/m² twice-daily [BID] for 5 days followed by 9 days of recovery) until disease progression or intolerable toxicity.

Oxaliplatin will be administered intravenously on day 1 of each treatment cycle (infusion duration: 2 hours), every 2 weeks. The first cycle will be administered at level -1 (70 mg/m²) and then increased to 85 mg/m² (if feasible) from the cycle 2 to 8 or until disease progression, whatever occurs first. In case of limitant-oxaliplatin neuropathy (see section 5.5.3) and in all cases after 8 cycles, oxaliplatin will be stopped and Trifluridine/Tipiracil will be continued alone until disease progression or intolerable toxicity.

ARM B: Comparator group (FOLFOX)

Folinic Acid 400 mg/m² (or 200 mg/m² if L-folinic acid) + oxaliplatin 85 mg/m² (infusion duration: 2 hours) followed by 5-FU bolus 400 mg/m² and then 5-FU 2400 mg/m² as a 46-hour continuous infusion. Treatment repeated every 14 days. In case of limitant-oxaliplatin neuropathy (see section 5.5.3) and in all cases after 8 cycles, oxaliplatin will be stopped and 5-FU (simplified LV5FU2 regimen) or capecitabine (1000 mg/m² BID during 2 weeks every 3 weeks) will be continued alone until disease progression or intolerable toxicity.

Protocol n°: UC-GIG-2203 EudraCT n°: 2022-000273-81

Treatment duration: The patient will be randomized in one of the two treatments arms and will receive their treatment every 14 days until disease progression or intolerable toxicity. Oxaliplatin will be stopped after 8 cycles or earlier in case of limitant-oxaliplatin neuropathy.

Dose escalation (if applicable): NOT APPLICABLE

E) STATISTICAL ANALYSIS PLAN

Required number of patients to be screened/included:

118 randomized patients (59 per arm)

Protocol n°: UC-GIG-2203 EudraCT n°: 2022-000273-81

STATISTICAL ANALYSIS:

Statistical analysis: randomized comparative phase II study.

Sample size justification

The study was calibrated to detect a treatment effect hazard ratio (HR) of 0.65 under the proportional hazards assumption, translating in an improvement in median PFS from 7.7 months (control arm) to 11.8 months (experimental arm).

With a 1:1 randomisation, a total of 97 events observed in the study would have 80% power to show statistically significant PFS at a 1-sided alpha level of 10%. Considering a recruitment duration of 36 months and a 24-month follow-up for the last included patient (estimated total duration of the study: 60 months), and assuming a common exponential dropout rate of 1%, 118 patients will be randomized in the study (59 patients by arm) so that maturity of the PFS data is approximately 82%.

Analysis populations

ITT Population: The ITT population is defined as all patients randomized in the trial.

Per-Protocol population: The Per-Protocol population is a subgroup of the ITT population containing all randomized patients with no major protocol violation who received at least one dose of study treatments.

Safety analysis set: The safety analysis is defined as all randomized patients having received at least one dose of study treatment, whether withdrawn prematurely or not.

Baseline characteristics and Efficacy endpoints will be described among the ITT population. The safety population will be used for safety analyses.

General methods

Qualitative variables will be described using frequency and percentage distributions. The number of missing data will be given, but will not be considered for the calculation of proportions. Quantitative data will be described using the number of observations, mean, standard deviation, median, minimum and maximum values. The date of randomisation will serve as a reference for calculation of durations unless otherwise indicated.

Statistical analyses will be performed using SAS® software version 9.4 or later.

Randomisation stratification:

Randomisation will be stratified on:

- PS 0-1 vs 2
- Age <75 vs ≥75

Timina

No interim analysis is planned. Final analysis will be performed after that required number of events (97 progression or death) are notified in order to ensure the expected statistical power and will be performed on frozen database after blind review.

Protocol n°: UC-GIG-2203 EudraCT n°: 2022-000273-81

Analysis methods

PFS will be estimated using the Kaplan-Meier method, and will be described in terms of median PFS and 1 year PFS rate, along with the associated 1-sided 90% confidence interval (CI; in accordance with sample size calculation) for the estimates.

OS will be estimated using the Kaplan-Meier method, and will be described in terms of median OS and 2-years OS rate, along with the associated 2-sided 95% CIs for the estimates.

PFS and OS analyses will be supplemented by a Cox model in order to measure the effect of the treatment throughout the follow-up (Hazard Ratio and its 95% CI).

Overall Response will be assessed according to RECIST v1.1 criteria. Percentage of responders will be presented with its 95% confidence interval.

Safety will be assessed in terms of AEs, SAEs and Toxic deaths. AE will be described according to MedDRA terms and graded according to CTCAE version 5.0. Descriptive statistics will be provided for characterizing and assessing patient tolerance to treatment.

Qol analysis will be performed according to the QLQ-C30 scoring manual provided by EORTC. Descriptive statistics will be used to summarize the scored scales at each scheduled assessment time point. Variation from baseline will be described.

F) SAMPLES COLLECTED FOR TRANSLATIONAL RESEARCH

Sample types: Tumour tissues and blood samples

Sample quantities:

Archived tumour tissues available will be collected for analysis (frozen and/or FFPE tissues) at baseline. Optional biopsy will be proposed to patients to collect tumour tissues at disease progression.

Blood samples will be collected for ctDNA testing: Blood samples will be collected at baseline before the experimental treatments and then every two months during the first year following randomisation or till disease progression, whatever occurs first. 30 mL of blood (5 EDTA tubes of 6 mL) will be collected at each sampling point (total: 210 mL of blood collected per patient)

Protocol n°: UC-GIG-2203 EudraCT n°: 2022-000273-81

G) TRIAL DURATIONS
Inclusion period: 36 months
Trial treatment period: 12 months
Follow-up: 12 months
Duration until primary endpoint evaluation: approximately 48 months
Overall trial duration (including follow-up): 60 months

H-SCHEDULE OF VISITS AND ACTIVITIES (SOA)

	Baseline	Visits during study treatment	End of Treatment (EOT) visit	Follow-up visits
	Within 14 days prior to first study treatment. Imagery can be done within 28 days prior to first study treatment	Day 1 of each cycle (delay ≤3 days allowed)	35 days (±5 days) after last study treatment	Every 8 (±2) weeks after EOT. Every 12 (±2) weeks after progressive disease
Consent signature	x			
Eligibility criteria	Х			
Randomisation	Х			
Diagnosis & prior anticancer therapies	Х			
Demographics, Medical history & signs and symptoms	Х			
Prior medication & concomitant medication	Х	Х	X	
Clinical exam (physical exam, PS) + vital signs ¹	Х	Х	Х	X ⁵
Glasgow and Modified Glasgow Prognostic Scores evaluation ⁶	Х			
Adverse events		Х	Х	Х
Electrocardiogram (ECG) ¹⁰	Х	Х		
Serology (HIV, hepatitis B/C)	Х			
Serum or urine pregnancy test (for all women of childbearing potential)	Х	X ¹¹	Х	
Complete Blood Count ²	Х	Х	Х	
Neutrophil/Lymphocyte Ratio (NLR) evaluation	Х			
Coagulation factors ³	Х			
Serum chemistries ⁴	x ⁷	х	Х	
Uracilemia	Х			
Tumour biomarkers (every 8 weeks from D1C5 till disease progression) - CEA and CA19-9	х	every 8 weeks from D1C5 till disease progression	Х	х
CT-Scan (Thorax, Abdomen, Pelvis) (every 8 weeks from D1C5 till disease progression)	х	every 8 weeks from D1C5 till disease progression	Х	Х
Tumour assessments (RECIST v1.1) (every 8 weeks from D1C5 till disease progression)	х	every 8 weeks from D1C5 till disease progression	Х	х
QoL questionnaire (QLQ-C30) (every 8 weeks from D1C5 till disease progression)	х	every 8 weeks from D1C5 till disease progression	Х	Х
G-CODE evaluation (only in patients ≥ 70 years) ⁸	Х	Х	Х	Х
Archived tumour material preparation and shipment	Х			

	Baseline	Visits during study treatment	End of Treatment (EOT) visit	Follow-up visits
	Within 14 days prior to first study		35 days (±5 days)	Every 8 (±2) weeks
	treatment. Imagery can be done	Day 1 of each cycle	after last study	after EOT. Every 12
	within 28 days prior to first study	(delay ≤3 days allowed)	treatment	(±2) weeks after
	treatment			progressive disease
Blood samples for ctDNA testing (5 EDTA tubes of 6 mL at each	x ⁹	every 8 weeks from D1C5 during the first year after randomisation or till disease		
sampling point)	-	progression, whatever occurs first)		
Optional tumour biopsy		at disease progression, before any new anticancer treatment initiation		

- 1) Vital signs: height, weight, blood pressure, pulse, body temperature. Height only at baseline.
- 2) CBC: haemoglobin, RBC counts, WBC and differential (neutrophils, eosinophils, basophils, monocytes, lymphocytes), platelets
- 3) Coagulation factors: partial thromboplastin time, fibrin, prothrombin ratio, sedimentation rate
- 4) Serum chemistries: Na, Ca, P, Mg, K, Cl, HCO3-, creatinine, urea, creatinine clearance, total protein, albumin, glucose, alkaline phosphatase, total and conjugated bilirubin, AST, ALT, LDH, γGT
- 5) During follow-up visits: only physical examination and evaluation of PS (vital signs are not to be done)
- 6) Glasgow and Modified Glasgow Prognostic Scores calculation method: see protocol Appendix 8
- 7) At baseline, in addition to parameters reported at item 4), serum chemistries must also include the C-reactive protein to allow Glasgow and Modified Glasgow prognostic scores calculation
- 8) G-CODE evaluation will be done at baseline, every 4 cycles during treatment, at the EOT visit and at the first follow-up visit (2 months after the EOT visit). For G-CODE evaluation method, please refer to protocol Appendix 9
- 9) If blood samples cannot be collected during the baseline visit, sampling can be done at Day 1 of Cycle 1 prior to any experimental treatment.
- 10) ECG at day 1 will be done prior and at the end of oxaliplatin infusion in both treatment arms
- 11) Pregnancy test will be performed monthly during all treatment period for women of childbearing potential

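### The haemoglobin entry limit in inclusion criterion 8 pairs a number and a unit that do not fit together, so as written it does not bind in practice

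*Protocol*

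**What the plan says.** In the Protocol summary, section C, Diagnosis and Inclusion criteria, item 8 is headed "Adequate organs function" and gives limits for neutrophils, platelets, haemoglobin, bilirubin, transaminases and creatinine clearance. The haemoglobin line reads "Haemoglobin ≥9 g/L".

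Three other places bear on it:

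- Item 7 of the same inclusion list uses the same unit for albumin: "denutrition defined by albumin <30 g/L".
- Footnote 2 to the schedule of visits (section H) names haemoglobin as a blood count parameter, "CBC: haemoglobin, RBC counts, WBC and differential", with no unit and no cut-off.
- Non-inclusion criterion 1 bars any "Patient with a performance status ECOG PS >2", so everyone screened successfully has PS 0, 1 or 2.

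Section E (Analysis populations) defines the Per-Protocol population as randomised patients without a major protocol violation who received at least one dose. It describes efficacy in the ITT population.

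**The concern.** An organ-function limit is there to separate patients who may enter from those who may not. Read literally, this one sits so low that it separates nobody who could realistically attend screening. The other limits in item 8 do not have this problem. The use of g/L for albumin one item earlier, at a plausible magnitude, shows that g/L is a unit the document does use and is not obviously a slip of notation throughout.

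Two things are at stake. The first is safety at entry. The population is frail by design (PS 2, or older age with a frailty criterion, or low albumin) and is about to start oxaliplatin-based chemotherapy, yet the written rule gives no working haemoglobin limit. The second is consistency. About 21 centres are planned, and a centre that reads the unit literally and one that silently corrects it would apply limits a factor of ten apart. A monitor who relies on the text has no basis for recording an eligibility deviation on this item, and so none for counting one as a major violation when the Per-Protocol set is drawn up.

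**Working it through.** **Inputs.** The threshold and unit are from inclusion criterion 8. The PS ceiling is from non-inclusion criterion 1. The design figures are from section E, Sample size justification.

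**Step 1: convert the unit.** 1 g/dL = 10 g/L.

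- As printed: 9 g/L ÷ 10 = 0.9 g/dL.
- The same number read in g/dL: 9 × 10 = 90 g/L.
- Ratio of the two readings: 90 ÷ 9 = 10.

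**Step 2: ask whether the printed limit can bind.** The documents give no distribution of haemoglobin, so no exclusion rate can be calculated. That 0.9 g/dL lies below anything seen in a patient well enough to be screened at PS 0 to 2 is general physiology, used here as an assumption. On that assumption the criterion is non-binding in practice.

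**Step 3: look for a correcting value.**

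| Place in the Protocol | What it gives for haemoglobin |
|---|---|
| Section C, inclusion criterion 8 | 9 g/L as a lower limit |
| Section C, non-inclusion criteria | nothing |
| Section H, schedule of visits, footnote 2 | listed as measured, no unit, no limit |

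No second value is available to confirm or override the first. That the cause is a g/dL versus g/L slip is therefore an inference, though a likely one.

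**Step 4: check that the design does not depend on it.** The plan is sized to "detect a treatment effect hazard ratio (HR) of 0.65" and states that "a total of 97 events observed in the study would have 80% power" at one-sided alpha of 10%. By Schoenfeld's formula for 1:1 allocation, the number of events is

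4 × (z for alpha + z for power)² ÷ (ln HR)² = 4 × (1.2816 + 0.8416)² ÷ (0.4308)² = 4 × 4.508 ÷ 0.1856 ≈ 97.2.

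This is 98 when rounded up, against 97 stated, and 97 events give 79.9% power. The plan's figure is reproduced within rounding, and haemoglobin enters nowhere in it.

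**The case against.** The strongest reply is that the value is so implausible that it corrects itself. An oncology investigator will notice it, and will query it or read it as g/dL. Haemoglobin is measured at baseline and on day 1 of each cycle, so a severely anaemic patient would not go unseen. This largely stands, and it is why the point is modest. It does not remove the point, because measuring a value is not the same as having a limit to judge it by, and a correction made in each reader's head is not something a monitor can enforce.

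A second reply is that the finding hangs on one character. A letter could have been lost when the file was converted, and the part of the protocol available here is the summary. It refers to a section 5.5.3 and to appendices that are not included, and a full eligibility section may print a different unit. None of this can be excluded. None of it is shown either, and the line as it stands is wrong.

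A third reply is that the trial's inference is untouched. This is correct. The same criterion applies before randomisation to both arms, so it introduces no bias between them, and efficacy is described in the ITT population.

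A reader might infer more: that sites have no reason to reinterpret the line, that an eCRF range check is coded to the literal value, or that severely anaemic patients have already been let in. The documents support none of these. The implausible number is itself a reason to reinterpret, no eCRF check on haemoglobin is described, and nothing shows that anyone has been enrolled under this text.

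**Conclusion.** The point holds as an error in an entry threshold. The printed limit equals 0.9 g/dL, is a tenth of what the same number would mean in g/dL, and is non-binding in practice. No other haemoglobin limit in the summary repairs it. The consequence is confined to eligibility screening, to uniformity across centres and to Per-Protocol membership. Harm to patients is a possibility under literal application and is not demonstrated.

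The conclusion rests on two assumptions: that the line is printed in the source as it appears here, and that no patient screened at PS 0 to 2 would have a haemoglobin as low as the printed figure. Its weight is that of a simple correction to a safety criterion. It would be wrong to present it as a flaw in the sample size or in the primary comparison.

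**What to change.** 1. Compare the line with the source document, and with the full eligibility section if that repeats it.
2. Have the medical team confirm the intended value and unit. This review proposes none.
3. Correct the line in the summary and wherever the protocol body or the eCRF carries it, so that all state the same value in the same unit.
4. If any patients were enrolled under the present text, check their baseline haemoglobin against the confirmed criterion. Any who fall below it can then be assessed consistently for the Per-Protocol set.

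The cost is a one-line correction, an update of any eCRF check that uses the value and, if enrolment has begun, a short listing of a variable that is already collected. The sample size and the planned analyses do not change.

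### CT/RECIST assessments are timed from Day 1 of cycle 5 and then from the end-of-treatment visit, while PFS runs from randomisation, so unequal treatment delays can bias PFS in either direction

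*Protocol*

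**What the plan says.** The primary endpoint section reads: "PFS defined as the time from the date of randomisation to date of disease progression (radiological or clinical) or death from any cause". Under General methods the protocol adds: "The date of randomisation will serve as a reference for calculation of durations unless otherwise indicated". Both make randomisation the origin.

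The schedule of visits and activities uses other origins for the assessments that date progression:

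- On treatment: "Tumour assessments (RECIST v1.1) (every 8 weeks from D1C5 till disease progression", in a column headed "Day 1 of each cycle (delay ≤3 days allowed". The CT row has the same timing.
- EOT visit, also with CT and RECIST: "35 days (±5 days) after last study treatment".
- Follow-up visits before progression, again with CT and RECIST: "Every 8 (±2) weeks after EOT", with a window of two weeks either way.

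The row label keeps cycle 5 as the origin while the follow-up column counts from EOT, and nothing says which governs. No assessment calendar from randomisation is given. The design is described as "Randomized, open label, comparative, multicentric, phase II trial". Both arms start on 14-day cycles. In the control arm, capecitabine in 3-week cycles is an option once oxaliplatin stops.

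**The concern.** A progression found on a scan is dated at that scan, so the scan calendar is part of how the primary endpoint is measured. Here the calendar depends on treatment. Day 1 of cycle 5 shifts with the interval from randomisation to first dose and with each postponement in cycles 1 to 4. The two arms receive different drugs in those cycles, and their oxaliplatin starting doses differ, so equal delays cannot be taken for granted.

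If one arm is delayed more, its progressions are found and dated later for reasons unrelated to the disease. The primary test already allows a one-sided error of 10%, and a scan that was taken late cannot be re-dated at analysis.

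**Working it through.** **1. The plan's own figures.** Inputs from Sample size justification: HR 0.65, one-sided alpha 10%, 80% power, 1:1 allocation.

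- Schoenfeld: events = 4 × (z₀.₉₀ + z₀.₈₀)² / (ln HR)² = 4 × (1.2816 + 0.8416)² / (0.4308)² = 97.2.
- With 97 events the power is 79.9%.
- 97/118 = 82%, the stated maturity.

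The design figures reproduce.

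**2. Where the scans fall on the protocol's own timings.**

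- Four 14-day cycles put Day 1 of cycle 5 at 4 × 14 = 56 days, week 8 after first dose, in both arms.
- Randomisation is in the baseline column, which allows up to 14 days before first treatment. Without any cycle delay, the first scan can therefore fall between 56 and 56 + 14 = 70 days after randomisation, weeks 8 to 10.
- A patient who stops before cycle 5 has no Day 1 of cycle 5. Counting from Day 1 of the last cycle, the EOT scan falls at about day 35 (week 5) after one cycle, or 42 + 35 = 77 days (week 11) after four.

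**3. Effect on the test.** Null trials were simulated with median PFS of 7.7 months in both arms, 59 patients per arm, 36-month accrual, the cut at the 97th event and a one-sided 10% log-rank test. Dropout was 1%, taken as per month because the protocol gives no unit. There were 6,000 runs per cell, so the Monte Carlo error is √(0.10 × 0.90 / 6000) ≈ 0.4 points.

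Assumed, because the protocol gives no figure:

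- the chance of a one-week delay at each of the four cycle starts up to cycle 5;
- the share of PFS events dated by a scan (100% or 70%), the rest being dated when they occur;
- scatter of half a week either way around each scan.

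The gap from randomisation to first dose and the EOT re-timing were left out. The mean difference at cycle 5 is 4 × (experimental − control), for example 4 × (0.40 − 0.10) = 1.2 weeks.

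Type I error (%), nominal 10:

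| Delay chance, exp. vs control | Mean difference (weeks) | Fixed calendar, 100% / 70% | From cycle 5, 100% / 70% | Every scan slips with cycles, 100% / 70% |
|---|---|---|---|---|
| 20% vs 20% | 0 | 10.3 / 10.4 | 9.4 / 10.6 | 10.5 / 11.1 |
| 30% vs 10% | 0.8 | 10.0 / 10.4 | 12.7 / 10.9 | 12.2 / 11.3 |
| 40% vs 10% | 1.2 | 10.2 / 10.7 | 13.8 / 11.6 | 12.8 / 11.9 |
| 50% vs 10% | 1.6 | 9.7 / 9.7 | 14.7 / 11.3 | 13.6 / 11.8 |
| 10% vs 40% | −1.2 | 10.1 / 10.5 | 7.6 / 9.2 | 7.2 / 9.1 |

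The column headed From cycle 5 is the literal reading: an 8-week calendar once cycle 5 has started. The last column applies if sites tie every scan to a cycle visit.

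Repeat simulations of the 40% against 10% case gave 12.4% (all events scan-dated) and 11.1% to 11.9% (70%); with the arms reversed they gave 7.3% to 8.4%. With 70% scan-dated, the smallest difference (10.9%) cannot be told from the equal-delay cell (10.6%).

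**The case against.** The strongest defence is that both arms share the same nominal grid, and that the protocol says nothing to suggest more delay in the experimental arm. That is right as far as it goes. A reader might infer that the schedule inflates the false-positive rate or favours the more toxic arm. The protocol supports neither: it gives no delay rates and does not say which arm is more toxic. Equal delays leave the test near 10%, and more delay in the control arm makes it conservative.

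Other stronger readings also fall short:

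- **EOT re-timing as a cause of inflation.** It brings an extra scan as well as a new origin, so an arm that stops more often may be scanned sooner. With unequal stopping and equal delays, simulated error was 9.6% to 10.4%. With 40% against 10% delay and all events scan-dated, adding EOT scans lowered it from 12.4% to between 10.9% and 11.5%. The unreconciled origins remain a drafting fault.
- **The capecitabine option.** Read literally, it does not move an 8-week calendar. If sites tied scans to 3-week cycles, control scans would be later, the conservative direction.
- **Clinical progression in an open-label trial.** PFS counts "date of disease progression (radiological or clinical) or death from any cause, whichever occurs first", but an excess of early clinical calls in one arm would have to be invented. A supportive analysis restricted to radiological progression can sit in an SAP. Deaths and clinical progressions are also not scan-dated, which dilutes the effect, as the 70% results show.
- **Larger error rates.** Shifting one arm's whole grid by the same amount, with no scatter, gives up to 18.8%. That result comes from every control event at a given scan preceding every experimental one. Real scan dates scatter.

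The 3-day allowance might be thought to rule delays out. It reads as a visit window, and nothing holds the scan date when a cycle is postponed. Even as a cap on each cycle, four would add up to 4 × 3 = 12 days, or 1.7 weeks.

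The mismatch of origins itself is not answered by any of this.

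**Conclusion.** The point holds as a design weakness of moderate, conditional size. Recorded progression dates depend on treatment timing, and PFS can be biased in either direction if the arms are delayed unequally. With the experimental arm later by an assumed 0.8 to 1.6 weeks on average at cycle 5, one-sided type I error is about 11% to 15%. The upper end requires every event to be scan-dated. With the control arm later by an assumed 1.2 weeks, it is about 7% to 9%, with a loss of power. These figures rest on the assumed delay probabilities, scan scatter and share of scan-dated events, none of which the protocol supplies. The change is worth making because it is cheap and removes the dependence on delays; it does not put the sample size in doubt.

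**What to change.** In the schedule of visits, time the CT and RECIST rows every 8 weeks from randomisation (weeks 8, 16, 24 and so on), with one fixed window in both arms, for example ±1 week. State that the calendar applies regardless of cycle number, cycle delay or treatment stop, until disease progression as the protocol already defines it. Refer the EOT and follow-up columns to the same calendar for patients who have not progressed, which also reconciles the two origins. Scanning need not be extended beyond the present definition of progression; doing so would add scans after clinical progression.

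In the simulations a calendar fixed from randomisation kept type I error between 9.7% and 10.7% in every delay scenario. The 97 events, 80% power and 118 patients stand. The cost is an edit to the schedule table and some scans that no longer coincide with a Day 1 or EOT visit.
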